3. GENERAL CONSIDERATIONS FOR DATA ANALYSES

The Final Analysis will include two sets of analysis: randomized phase analysis and all B/F/TAF analysis. All table summaries in this final analysis will be based on data included in the All B/F/TAF analysis (eg, data collected during the study period when participants were on B/F/TAF).

Randomized phase analysis (eg, including data collected during double-blind phase when participants were on the double-blind study drug), and the corresponding analysis window defined in Section 3.8, will be used to support applicable listings where data collected from the double-blind phase are indicated. The wording of randomized phase or double-blind phase might be used interchangeably throughout the SAP and in the TFLs.

Randomized Phase Analysis:

- For participants who are never treated in the extension phase of the study, including those who prematurely discontinue the randomized study drug or who complete the randomized study drug and do not receive any dose of B/F/TAF in the extension phase, all available data will be included in the randomized phase analysis.
- For participants who complete the randomized phase and receive at least 1 dose of B/F/TAF in the extension phase, the randomized phase analysis will include (1) all available AE, concomitant medication, pregnancy, and death data collected prior to the extension phase first dose date; (2) all available other data, such as laboratory, vital sign, electrocardiogram (ECG), collected on or prior to the extension phase first dose date.

All B/F/TAF Analysis:

- For participants who receive B/F/TAF in the randomized phase, all available data for participants who actually receive B/F/TAF in the randomized phase will be included.
- For participants who actually receive DTG + F/TDF in the randomized phase and receive at least 1 dose of B/F/TAF in the extension phase, (1) all available AE, concomitant medication, pregnancy, and death data with start date **on or after** the first dose date of B/F/TAF in the extension phase and (2) all available other data, such as laboratory, vital sign, and ECG data, collected **after** the first dose date of B/F/TAF in the extension phase will be included. The data collected **on or prior to** the first dose date of B/F/TAF will be used to derive the baseline value for the all B/F/TAF analysis.

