7.1.5. Treatment-Emergent Adverse Events

7.1.5.1. Definition of Treatment-Emergent Adverse Events

Treatment-emergent adverse events (TEAEs) are defined as 1 or both of the following:

- Any AEs with an onset date on or after the study drug start date and no later than 30 days after permanent discontinuation of the study drug, or
- Any AEs leading to premature discontinuation of study drug.

For the all B/F/TAF analysis, the AE onset date will be compared with the first and last dose dates for the All B/F/TAF phase analysis.

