7.5. Concomitant Non-Antiviral Medications

Concomitant non-antiviral medications (ie, medications other than study drug, and antiviral drugs that are taken while receiving study drug) will be coded using the WHO Drug Dictionary. The WHO preferred name and drug code will be attached to the clinical database. Use of concomitant medications from Study Day 1 for All B/F/TAF analysis up to the date of last dose of study drug will be summarized (number and percentage of participants) by treatment group and generic name (preferred drug name). Multiple drug use will be counted only once per participant. The summary will be sorted by decreasing order of total frequency of medication generic name.

If the start or stop date of non-antiviral medications is incomplete, the month and year (or year alone, if month is not recorded) of the start or stop date will be used to determine whether the non-antiviral medications are concomitant or not. The medication is concomitant if the month and year of the start or stop (or year of the start or stop, if month is not recorded) of the medication does not meet either of the following criteria:

- The month and year of start of the medication is after the date of the last dose of study drug
- The month and year of stop of the medication is before the date of the first dose of study drug

If the start and stop date of non-antiviral medications are complete, the start date is not after last dose date and the stop date is not before first dose date, or the non-antiviral medications are marked as ongoing and start date is on or before last dose date, the non-antiviral medications are concomitant.

Summaries of non-antiviral concomitant medications will be provided for the All B/F/TAF Safety Analysis Set. Participants with any non-antiviral concomitant medications will be listed. No inferential statistics will be provided.

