	Serum Sodium	Decrease	Serum Sodium (Hyponatremia)
	Total Bilirubin	Increase	Total Bilirubin (Hyperbilirubinemia)
	Total Cholesterol (Fasting)	Increase	Total Cholesterol (Fasting, Hypercholesterolemia)
	Triglycerides (Fasting)	Increase	Triglycerides (Fasting, Increased)
	LDL (Fasting)	Increase	LDL (Fasting, Increased)
	Urea Nitrogen (BUN)	Increase	Urea Nitrogen (Increased)
	Uric Acid	Increase	Uric Acid (Hyperuricemia)
	Uric Acid	Decrease	Uric Acid (Hypouricemia)
	Prothrombin Intl. Normalized Ratio (INR)	Increase	N/A
	Prothrombin Time (PT)	Increase	N/A
Urinalysis	Urine Blood	Increase	N/A
· · ·	Urine Glucose	Increase	Urine Glucose (Glycosuria)
	Urine Protein	Increase	Urine Protein (Proteinuria)
	Urine RBC	Increase	Urine RBC (Hematuria, Quantitative)

Note: Prothrombin Intl. Normalized Ratio (INR) and Prothrombin Time (PT) were graded based on the protocol defined toxicity grade scale. The results and toxicity grade will be listed in listing, but not be summarized in lab toxicity summary table.

- 15. Concomitant nonstudy-drug ARV medications (for all B/F/TAF analysis (ie, ARV medications other than study drug that are taken while receiving study drug B/F/TAF) will be flagged in "Nonstudy-Drug Antiviral Medication" listing. The logic to define concomitant nonstudy-drug ARV is similar to concomitant non-ARV Medications (see details in Section 7.5)
- 16. Lipid modifying medication analyses for All B/F/TAF analysis:

Lipid modifying medication is defined to be the concomitant medication with ATC2 term = "LIPID MODIFYING AGENTS" and CMDECOD contains wording of "STATIN" in the ADCM dataset.

Subjects who took lipid modifying medications at first dose of B/F/TAF (including both phases) refer to the subjects who use of the lipid modifying agents at study day 1 of all B/F/TAF analysis. More specifically, subjects with "Lipid Modifying Agent Use at First Dose of B/F/TAF" include those subjects in all B/F/TAF analysis set with: 1) any selected CM record with the start date \leq the first dose date of B/F/TAF (including both phases), and 2) the end date of the selected CM record \geq the first dose date of B/F/TAF (including both phases).

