20. The TEAE definitions will be applied to the double-blind randomized phase data and the OL extension phase data, separately. When randomized phase data are used, AEs onset date will be compared with the randomized phase first dose date and last dose date and premature discontinuation of study drug refers to study drug discontinuation in the randomized phase. An AE meeting the TEAE criteria will be considered as a TEAE in the randomized phase. When OL extension phase data are used, AEs onset date will be compared with the extension phase first dose date and last dose date and premature discontinuation of study drug refers to study drug discontinuation in the extension phase. AE meeting the TEAE criteria will be considered as a TEAE in the OL extension phase.

One AE will be included either in the double-blind randomized phase or OL extension phase, but not both, except that an AE is treatment-emergent in the randomized phase, but continuing into extension phase and leading to prematurely discontinuation of the study drug in the extension phase, which will be counted as treatment-emergent for both phases. When an AE with missing onset date and according to the following rules for incomplete dates, an AE is treatment emergent in the OL extension phase, then the AE will be included in OL extension phase and considered treatment emergent in OL extension phase only.

Events with Missing Onset Day and/or Month

An AE is treatment emergent if the following 3 criteria are met:

- 1) The month and year (or year) of onset date is the same as or after the month and year (or year) of the first dose of study drug, and
- 2) The month and year (or year) of the onset date is the same as or before the month and year (or year) of the 30th day after the date of the last dose of study drug, and
- 3) End date is as follows:
 - a) The (complete) end date is on or after the first dose date, or
 - b) The month and year (or year) of end date is the same or after the month and year (or year) of the first dose of study drug, or
 - c) End date is completely missing

Events with Completely Missing Onset Date

An AE with a completely missing onset date is defined as TEAE if end date meets any of the criteria specified in 3) above.

SAP-Final-GS-US-380-4458

ELECTRONIC SIGNATURES

Signed by	Meaning of Signature	Server Date (dd-MMM- yyyy hh:mm:ss)
PPD	Global Development Lead (GDL) eSigned	10-Apr-2024 00:34:58
PPD	Biostatistics eSigned	10-Apr-2024 14:18:07

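### For participants who switch to B/F/TAF, the start-date filter in SAP Section 3 conflicts with the SAP's own rules for concomitant medications, lipid agents and adverse events that end B/F/TAF

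*SAP*

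**What the plan says.** SAP Section 3 sets out what enters the All B/F/TAF analysis. Participants who received B/F/TAF from randomization contribute everything available. Participants who switched from DTG + F/TDF contribute "all available AE, concomitant medication, pregnancy, and death data with start date" on or after the first extension dose of B/F/TAF. Data from on or before that dose may be used to derive the baseline value, and no other use is mentioned. The same section fixes the reach of the rule: "All table summaries in this final analysis will be based on data included in the All B/F/TAF analysis".

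Three later rules in the SAP concern the same records:

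- **Section 7.5, concomitant non-antiviral medications.** "Use of concomitant medications from Study Day 1 for All B/F/TAF analysis up to the date of last dose of study drug will be summarized". For switchers, Section 3.8.1 places Study Day 1 at the first extension dose. With complete dates, a medication is concomitant when "the start date is not after last dose date and the stop date is not before first dose date".
- **Section 7.2.3 and Appendix 7 item 16, lipid-modifying agents.** A summary is planned of use at the first B/F/TAF dose and of initiation while on B/F/TAF. Use at first dose needs "any selected CM record with the start date" on or before that dose and an end date on or after it. Anyone who took such an agent before the first B/F/TAF dose is not an initiator.
- **Section 7.1.5.1 and Appendix 7 item 20, treatment-emergent adverse events.** The second limb of the definition is "Any AEs leading to premature discontinuation of study drug", with no condition on onset. Section 3 says that study drug here means B/F/TAF. Item 20 addresses an event that is treatment-emergent in the randomized phase, continues, and ends up "leading to prematurely discontinuation of the study drug in the extension phase, which will be counted as treatment-emergent for both phases".

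**The concern.** The three later rules need records that the Section 3 filter takes out of the switch group. A programmer who builds the All B/F/TAF dataset from Section 3 and then applies the later definitions cannot recover those records.

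The accuracy of the switch column is at stake in three places: the concomitant medication table, the lipid-agent summary, and the treatment-emergent adverse event tables, including the one in Section 7.1.6 for events that caused premature discontinuation. The B/F/TAF column has no such filter, so two columns of one table would follow different admission rules.

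**Working it through.** No sample size, power or error-rate figure bears on this point, and the plan states no figure to reproduce. The check is to write each rule as a condition and compare the rules on test records for one switcher.

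**Inputs.** The first extension dose F is set at day 0 for convenience. The last dose L is set at day 336 for illustration (48 weeks × 7). A record has start s and end e.

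- Section 3 admits a record if s ≥ F.
- Section 7.5 calls a medication concomitant if s ≤ L and e ≥ F.
- Item 16 counts use at first dose if s ≤ F and e ≥ F.
- Section 7.1.5.1 counts an adverse event if F ≤ onset ≤ L + 30 (that is, 0 to 366), or if it leads to premature discontinuation of B/F/TAF.

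**Medications**

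| Record | Section 3 | 7.5 | Item 16, at first dose |
|---|---|---|---|
| Day −100 to day −5 | out | out | out |
| Day −100 to day 0 | out | **in** | **in** |
| Day −100 to day 50 | out | **in** | **in** |
| Day −100, ongoing | out | **in** | **in** |
| Day 0, ongoing | in | in | in |
| Day 30 to day 60 | in | in | out |
| Day 400, ongoing | in | out | out |

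Rows 2 to 4 are the conflict: a drug started before the switch and still in use on or after the switch day. In the last two rows Section 3 admits a record that a later rule then leaves out, which is harmless. For use at first dose, meeting both s ≥ F and s ≤ F requires s = F. Among fully dated records, only an agent started on the switch day itself survives.

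**Prior-use check in item 16.** Take a switcher with a statin record from day −100 to day −5 and a second record starting on day 30. Item 16 says prior user, so not an initiator. Under Section 3 only the second record is visible, so the participant counts as an initiator. Replacing Section 3 with the 7.5 overlap rule does not cure this, because the first record (e = −5 < 0) is still dropped.

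**Adverse events**

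| Event | Section 3 | 7.1.5.1 |
|---|---|---|
| Onset day −50, drug not stopped | out | out |
| Onset day −50, ends extension B/F/TAF | out | **in** |
| Onset day 0, drug not stopped | in | in |
| Onset day 20, ends extension B/F/TAF | in | in |
| Onset day 400, drug not stopped | in | out |

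Row 2 is the only class that Section 3 loses and 7.1.5.1 wants. It is the case item 20 describes. Ordinary pre-switch events are excluded by both rules, as they should be.

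**Where the lost event would still appear.** Section 4.1.2 tabulates reasons for stopping study drug in the extension. Section 7.1.6 lists all adverse events and those leading to discontinuation. Section 3 says most listings cover all randomized participants and both phases. The event is therefore missing only from the treatment-emergent tables, and the disposition and adverse event tables of one report could disagree.

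**The case against.** The strongest reply is that Section 3 is a general section and the later rules are specific. Item 16 speaks of B/F/TAF in both phases and would be nearly empty for switchers if Section 3 were applied first. Section 7.5 has a complete overlap definition, and item 20 spells out the carry-over event. Section 3.1.3 also admits safety data from both phases up to 30 days after B/F/TAF ends. A sensible programmer might let the specific rules govern.

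That reading is plausible, but the SAP never states it. Section 3.1.3 makes room for exceptions; the start-date filter in Section 3 has no such clause. Taken as an override, Section 3.1.3 would readmit everything recorded on DTG + F/TDF, which cannot be meant. The sentence about baseline values might be stretched to lipid use at first dose, but not to 7.5 or to adverse events.

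Four stronger conclusions might be drawn, and the documents do not support them:

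- **That discontinuations of B/F/TAF vanish from the report.** They remain in disposition and in listings.
- **That lipid-agent use at first dose must be zero.** Agents started on the switch day count. Item 16 also treats a completely unknown start as on or before first dose, and Section 3 does not say how to filter such a record.
- **That the tables are wrong by a known amount.** The shortfall equals the true prevalence of earlier-started use. Assuming 5 to 20% only returns 5 to 20 points. The documents give neither that prevalence nor the number of switchers.
- **That trial conclusions are affected.** Section 3 plans no comparison between groups in this analysis, and Section 6 says the Week 48 and Week 96 endpoints are already reported. Some difference between the columns is also intended, since switchers' earlier data were collected on the comparator.

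**Conclusion.** The conflict is real and is confined to the DTG + F/TDF to B/F/TAF group. If Section 3 is applied first, four things follow for that column:

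1. Concomitant medications already in use at the switch are under-reported.
2. Lipid-agent use at first dose is almost nil among fully dated records.
3. A prior lipid-agent user with a new record after the switch can be counted as an initiator.
4. Adverse events that began before the switch and ended B/F/TAF are missing from the treatment-emergent tables.

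This rests on reading Section 3 as written. If the programming already lets the later rules prevail, the tables are right and only the text is inconsistent. The effect is descriptive, with no test or error rate involved, and its size cannot be derived from the documents. It is worth correcting because the literal rule gives wrong counts and the correction is nearly free.

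**What to change.** Amend the switcher bullet in SAP Section 3 with three clauses:

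1. Include concomitant medications by overlap with B/F/TAF exposure, as in Section 7.5: start on or before the last B/F/TAF dose, and stop on or after the first B/F/TAF dose or ongoing.
2. Keep all lipid-modifying records from before the switch, including those that ended before it, for the at-first-dose and prior-use checks in Appendix 7 item 16. The overlap rule alone would drop stopped agents and miscount a restart as an initiation.
3. Include adverse events that start on or after the first B/F/TAF dose, plus any adverse event leading to premature discontinuation of B/F/TAF whatever its start date, as Section 7.1.5.1 and item 20 already state.

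The cost is a few lines of wording and a change to a dataset filter. No new data are needed. If the SAP is already final, Section 1 provides for recording the change in the clinical study report.

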3.1. Analysis Sets

Analysis sets define the participants to be included in an analysis. Analysis sets and their definitions are provided in this section. Participants included in each analysis set will be determined before the study blind is broken for analysis. The analysis set will be included as a subtitle of each table, figure, and listing. A summary of the number and percentage of participants in each analysis set will be provided by treatment group and in total.

3.1.1. All Randomized Analysis Set

The **All Randomized Analysis Set** will include all participants who are randomized into the study. This is the primary analysis set for by-participant listings.

3.1.2. All B/F/TAF Full Analysis Set

The **All B/F/TAF Full Analysis Set** will include all participants who (1) are randomized into the study, (2) have received at least 1 dose of the B/F/TAF in the randomized phase or at least 1 dose of the B/F/TAF in the extension phase, and (3) have at least 1 post baseline HIV-1 RNA or HBV DNA results while on B/F/TAF. This is the primary analysis set for the all B/F/TAF efficacy analyses.

For efficacy analyses, all efficacy data collected for the all B/F/TAF analysis will be included, unless specified otherwise.

3.1.3. All B/F/TAF Safety Analysis Set

The All B/F/TAF Safety Analysis Set will include all participants who (1) are randomized into the study and (2) have received at least 1 dose of the B/F/TAF in the randomized phase or at least 1 dose of the B/F/TAF in the extension phase. This is the primary analysis set for the all B/F/TAF safety analyses.

For safety analyses, all safety data collected up to 30 days after permanent discontinuation of B/F/TAF (including randomized and open label phases) will be included in the safety summaries, unless specified otherwise.

3.1.4. All B/F/TAF Serologically Evaluable Full Analysis Set

3.1.4.1. All B/F/TAF Serologically Evaluable Full Analysis Set for HBsAg Loss/Seroconversion

The All B/F/TAF Serologically Evaluable Full Analysis Set for HBsAg loss/seroconversion includes all participants who were in the All B/F/TAF Full Analysis Set, and with HBsAg positive and HBsAb negative or missing at baseline.

3.1.4.2. All B/F/TAF Serologically Evaluable Full Analysis Set for HBeAg Loss/Seroconversion

The All B/F/TAF Serologically Evaluable Full Analysis Set for HBeAg loss/seroconversion includes all participants who were in the All B/F/TAF Full Analysis Set, and with HBeAg positive and HBeAb negative or missing at baseline.

3.2. Participant Grouping

For analysis using the All Randomized Analysis Set, participants will be grouped by the randomized treatment (labeled as B/F/TAF vs. DTG + F/TDF).

For all analyses included in the all B/F/TAF analysis, participants will be grouped into the following 2 groups:

- B/F/TAF group: This group includes all participants who actually received B/F/TAF in the randomized phase of this study, regardless whether participants receive any B/F/TAF in the extension phase or not.
- DTG + F/TDF to B/F/TAF group: This group includes all participants who actually received DTG + F/TDF regimen in the randomized phase of this study and then receive at least 1 dose of B/F/TAF in the extension phase.

3.3. Strata and Covariates

Randomization was stratified by HBeAg (positive vs. negative), HBV DNA (< $8 \log_{10} IU/mL$ vs $\geq 8 \log_{10} IU/mL$), CD4+ cell count (< $50 \text{ cells/}\mu L$ vs $\geq 50 \text{ cells/}\mu L$) at screening.

3.4. Examination of Participant Subgroups

3.4.1. Participant Subgroups for Safety Analyses

Selected safety endpoints (eg. AEs and liver-related laboratory tests) may be analyzed for the following participant subgroups (see Section 8.1 for details):

- Participants with HIV/HBV/hepatitis C virus (HCV) coinfection at baseline
- Participants with incident HIV/HBV/HCV coinfection while on study drug (if any)

3.5. Multiple Comparisons

No alpha level adjustment is applied other than for the primary endpoints at Week 48.

3.6. Missing Data and Outliers

3.6.1. Missing Data

A missing datum for a given study analysis window may be due to any of the following reasons:

- A visit occurring in the window but data were not collected or were unusable
- A visit not occurring in the window
- A participant prematurely discontinuing from the study before reaching the window

In general, values for missing data will not be imputed, unless methods for handling missing data are specified.

For missing last dosing date of study drug, imputation rules are described in Section 3.8.1. The handling of missing or incomplete dates for AE onset is described in Section 7.1.5.2, and for concomitant medications in Section 7.5.

3.6.2. Outliers

Outliers will be identified during the data management and data analysis process, but no sensitivity analyses will be done to evaluate the impact of outliers on efficacy or safety outcomes, unless specified otherwise. All data will be included in the analyses.

3.7. Data Handling Conventions and Transformations

The following conventions will be used for the imputation of date of birth when it is partially missing or not collected:

- If only month and year of birth is collected, then "15" will be imputed as the day of birth
- If only year of birth is collected, then "01 July" will be imputed as the day and month of birth
- If year of birth is missing, then date of birth will not be imputed

In general, age collected at Day 1 (in years) will be used for analyses and presented in listings. If age at Day 1 is not available for a participant, then age derived based on date of birth and the Day 1 visit date will be used instead. If an enrolled participant was not dosed with any study drug, the randomization date will be used instead of the Day 1 visit date. For screen failures, the date the first informed consent was signed will be used for the age derivation. Age required for longitudinal and temporal calculations and analyses (eg, estimates of creatinine clearance, age at date of AE) will be based on age derived from date of birth and the date of the measurement or event, unless otherwise specified.

Non-PK data that are continuous in nature but are less than the lower limit of quantitation or above the upper limit of quantitation will be imputed as follows except for urine creatinine:

- A value that is 1 unit less than the limit of quantitation will be used for calculation of descriptive statistics if the datum is reported in the form of "< x" (where x is considered the limit of quantitation). For example, if the values are reported as < 50 and < 5.0, values of 49 and 4.9, respectively, will be used for calculation of summary statistics. An exception to this rule is any value reported as < 1 or < 0.1, etc. For values reported as < 1 or < 0.1, a value of 0.9 or 0.09, respectively, will be used for calculation of summary statistics.
- A value that is 1 unit above the limit of quantitation will be used for calculation of descriptive statistics if the datum is reported in the form of "> x" (where x is considered the limit of quantitation). Values with decimal points will follow the same logic as above.
- The limit of quantitation will be used for calculation of descriptive statistics if the datum is reported in the form of " \leq x" or " \geq x" (where x is considered the limit of quantitation).

For urine creatinine, a value of "< 1" is handled as a missing value in its summary and the calculation of related ratios.

Logarithmic (base 10) transformations will be applied to HIV-1 RNA and HBV DNA data for efficacy analyses. HIV-1 RNA results of 'No HIV-1 RNA detected' and "<20 cp/mL HIV-1 RNA Detected" will be imputed as 19 copies/mL for analysis purposes.

HBV DNA results of "<20 IU/mL HBV DNA detected" or "No HBV DNA detected" will be imputed as 19 IU/mL for analysis purposes. For the Cobas 6800 Assay for HBV DNA, "<10 IU/mL HBV DNA detected" or "No HBV DNA detected" will be imputed as 9 IU/mL for analysis purposes.

For data from a local laboratory, data would be treated as missing data if its reported unit is missing but its corresponding unit from a central laboratory is not missing, or its reported unit is not missing but a value in conventional unit is missing (due to no confirmed unit conversion formula available).

